### **Analyses:**

- Descriptive statistics of the actual values and the change from baseline per parameter over time according to the specification described in section 2.6 will be included.
- A cross-tabulation of the worst toxicity grades versus baseline parameter and per analysis phase/period will be presented including also the number of subjects per worst grade, the number of subjects with treatment emergent worst grades per grade and the cumulative number of subjects.
- A cross-tabulation of the worst abnormalities versus baseline per parameter and analysis phase/period will be presented including also the number of subjects per abnormality, the number of subjects with treatment emergent abnormalities per abnormality.
- A tabulation of percentage and number of the subjects who have treatment-emergent worst toxicity grades per parameter and analysis phase/period will be included.

---

- A tabulation of percentage and number of the subjects who have treatment-emergent worst abnormalities per parameter and analysis phase/period will be included.
- A listing including all parameters with at least one treatment-emergent toxicity or abnormality per subject (exclusion of urinalysis) is provided.
- All results of the hepatic parameters per subject for subjects with at least one treatment-emergent abnormality/toxicity within these hepatic parameter results is included in a listing.
- A listing including all parameters with at least one grade 3 treatment-emergent toxicity per subject (exclusion of urinalysis) is presented.
- A listing with abnormal urinalysis results and a listing including all urinalysis data will be provided.
- The actual values over time are plotted per the laboratory parameter. Each line will represent one subject.
- Mean (+/- SE) plots of the actual values for alanine transferase will be presented.
- Mean (+/- SE) plots of the change from baseline for alanine transferase will be presented.

### **6.3.    Electrocardiogram**

Twelve-lead triplicate ECGs are collected throughout the trial. Evaluation of the triplicate 12-lead ECGs will be based on the mean value of the triplicate parameters and the abnormalities will be defined on the triplicate means. Only data from the ERT vendor will be analyzed. All other data will be listed.

The following ECG parameters measurements will be analyzed:

- PR interval (ms)
- Heart Rate (bpm)
- QT interval (ms)
- QRS duration (ms)
- QTc Corrected (Fridericia's formula QTcF)
- QTc corrected (Bazett's formula QTcB)

#### **Triplicate ECG assessments:**

For the time points on which triplicate ECGs apply, a rounded mean value per triplet will be calculated per time point and equal EGGRPID before any further handling. This rounded

---

mean value will be used through the entire analysis. In case a ‘triplicate’ has a missing record or additional records, an average will be taken nevertheless. The date time of the first record of the triplicate will be included for the mean value.

Any rounding will be performed after computation of the applicable parameters, and before any further handling.

#### **Imputation rules / calculation of derived parameters:**

ECG records with missing assessment date parts (any day/month/year) will not be used in analysis, except in the listings.

If heart rate (HR) is missing, it will be calculated using RR (if available) and rounded to the integer value (see formula below) before any further handling if applicable.

$$\frac{1000}{RR(ms)} = \frac{HR(bpm)}{60}$$

HR from the vital signs section (i.e. pulse) will not be used in this ECG analysis section.

Note: RR values (if available) will only be listed. Recalculated HR values will be flagged.

Corrected QT (Bazett’s and Fridericia’s formula) are not calculated as this is provided in the datasets.

#### **Abnormalities for ECG parameters:**

The abnormalities in ECG parameters will be determined according to the criteria specified in the Cardiovascular Safety – Abnormalities Table (see [APPENDIX 8](#)). Abnormalities on actual values are provided for HR, PR, QRS, QTcF and QTcB. Additional, abnormalities on change from baseline will be provided for QTcB and QTcF.

No abnormalities will be defined for actual uncorrected QT values. Uncorrected QT  $\geq 500$  ms will be flagged and only shown in listings.

Note: the QTc definitions for abnormalities follow the ICH E14 guidance .

---

### **Treatment-emergent definition for abnormalities:**

An assessment is treatment-emergent if /abnormality worsened as compared to the abnormality at baseline; this also includes the shift from abnormally high to abnormally low and vice-versa. Post-reference abnormalities are always treatment-emergent with regard to missing abnormalities at baseline. The abnormally high abnormalities (i.e. abnormally high, borderline prolonged, prolonged, pathologically prolonged) versus the abnormally low are considered equally important.

Abnormalities defined on changes from baseline are always treatment-emergent.

### **Worst abnormality determination:**

A worst-case analysis time point will be created for parameters for which abnormalities are defined to summarize values considered as the worst-case. For abnormalities, it is derived per parameter and in case both the lowest and the highest values are considered abnormal, a subject can have two worst-case analysis visits for a same parameter within each phase/period. Worst-case will be derived within each phase/period, including unscheduled assessments.

### **Analyses:**

- Descriptive statistics of the actual values and the change from baseline per parameter (all parameters except for RR) over time according to the specification described in section 2.6 will be included.
- A cross-tabulation of the worst abnormalities (on actual values) versus baseline per parameter (i.e. for HR, PR, QRS, QTcB and QTcF) and analysis phase/period will be presented including also the number of subjects per abnormality, the number of subjects with treatment emergent abnormalities per abnormality.
- A tabulation of percentage and number of the subjects who have treatment-emergent worst abnormalities per parameter (i.e. for HR, PR, QRS, QTcB and QTcF) and analysis phase/period will be included.
- A cross-tabulation of the worst change from baseline abnormalities (i.e. for QTcB and QTcF) versus the actual value per parameter and analysis phase/period will be presented including also the number of subjects per abnormality, the number of subjects with treatment emergent abnormalities per abnormality.

---

- A listing including all parameters (i.e. no findings) for subjects with at least one treatment-emergent abnormality (on actual values or change from baseline) is provided.
- A listing including all findings (e.g. interpretation, rhythm, technical findings) is provided.
- A listing including all parameters (i.e. no findings) for subjects with uncorrected QT values  $\geq 500$  ms is provided.
- The actual values over time are plotted per ECG parameter. Each line will represent one subject.
- A frequency tabulation of categorized corrected QT change from baseline per treatment and per timepoint will be presented. ( $\leq 30$  msec,  $> 30 - \leq 60$  msec,  $> 60$  msec)
- A frequency tabulation of categorized corrected QT interval values per treatment group and per timepoint will be presented. ( $\leq 450$  msec,  $> 450 - \leq 480$  msec,  $> 480 - \leq 500$  msec,  $> 500$  msec)

## **6.4. Vital Signs**

The following vital signs parameters measurements will be analyzed:

- Supine pulse rate (bpm)
- Supine systolic blood pressure (mmHg)
- Supine diastolic blood pressure (mmHg)
- Body temperature

For body temperature, only baseline and week 20 will be seen as planned time points. All locations of measurement (e.g. forehead, oral, tympanic) will be taken into account for body temperature as a single parameter. All measurements will be taken into account for the worst-case analysis time point determination.

### **Imputation rules:**

Vital signs records with missing assessment dateparts (any day/month/year) will not be used in the analysis but will be listed.

### **Abnormalities for vital signs parameters:**

---

The abnormalities in vital signs will be determined according to the criteria specified in the Cardiovascular Safety – Abnormalities Table ([APPENDIX](#) ).

### **Treatment-emergent definition for toxicity grades and abnormalities:**

An assessment is treatment-emergent if /abnormality worsened as compared to the abnormality at baseline; this also includes the shift from abnormally high to abnormally low and vice-versa. Post-reference abnormalities are always treatment-emergent with regard to missing abnormalities at baseline. The abnormally high abnormalities (i.e. abnormally high, grade 1 or mild, grade 2 or moderate, grade 3 or severe) versus the abnormally low are considered equally important.

### **Worst abnormality determination:**

A worst-case analysis time point will be created for parameters for which abnormalities are defined to summarize values considered as the worst-case. For abnormalities, it is derived per parameter and in case both the lowest and the highest values are considered abnormal, a subject can have two worst-case analysis visits for a same parameter within each phase/period. Worst-case will be derived within each phase/period, including unscheduled assessments.

### **Analyses:**

- Descriptive statistics of the actual values and the change from baseline per parameter over time according to the specification described in section 2.6 will be included.
- A cross-tabulation of the worst abnormalities versus baseline per parameter and analysis phase/period will be presented including also the number of subjects per abnormality, the number of subjects with treatment emergent abnormalities per abnormality.
- A tabulation of percentage and number of the subjects who have treatment-emergent worst abnormalities per parameter and analysis phase/period will be included.
- A listing including all parameters for subjects with at least one treatment-emergent abnormality (on actual values or change from baseline) is provided.
- The actual values over time are plotted per vital signs parameter. Each line will represent one subject.

---

## 6.5. Physical Examination

The physical examination records and abnormalities will be listed.

## 7. VIRAL GENOME SEQUENCE ANALYSIS

Viral genome sequence analysis will be performed to identify pre-existing baseline polymorphisms and to evaluate emergence of mutations associated with JNJ-56136379 and/or ETV or TDF treatment.

Sequencing of the HBV genome will be performed to monitor HBV variants present at the time points indicated in section 7.1 (see [APPENDIX 5](#) and [APPENDIX 6](#) for details).

Virology results will be presented by specified timepoints and genetic region and position of interest. A separate virology report will be performed by the virologist.

### 7.1. Time Points and Samples

When analyzing virology parameters, the focus will be on genetic variants at

- Time Point of Sequence at Baseline (BLSEQ): Last available pre-dose time point in the study with virology data available
- Time Point of Sequence at end of JNJ-379 treatment (last available on-treatment time point)
- Time Point of Sequence at Viral Breakthrough: time point with virology data available closest to the time point of viral breakthrough (FTPT) See section 5.3.1 for viral breakthrough definition
- Time Point of Sequence at Viral Relapse: time point with virology data available closest to the time point of viral relapse See section 5.3.1 for viral relapse definition
- Time Point of Sequence at End of Study (ESSEQ): last available off-treatment post-baseline time point in the study with virology data available
- Aggregated Post-Baseline Study Period (ASSEQ): entire post-baseline study period, aggregate of all available time points in the study with virology data available

---

- Aggregated Post-Baseline Treatment Period (ATSEQ): entire post-baseline treatment period, aggregate of all available post-baseline time points during the treatment phase with virology data available

The sequencing of samples after baseline may be triggered by the sponsor virologist based on changes in HBV DNA levels observed in each individual subject and the limits of the sequencing assay.

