Treatment with JNJ-56136379 may lead to emergence of viral variants with reduced susceptibility or resistance to JNJ-56136379. Based on pre-clinical data, these variants remain susceptible to TDF and ETV but might affect treatment options with CAMs in the future.

As of 6 February 2019, virological breakthrough, as defined by the protocol (ie, confirmed on-treatment HBV DNA increase  $>1 \log_{10}$  from nadir level or confirmed on-treatment HBV DNA level  $>200$  IU/mL in subjects who had HBV DNA level below the LLOQ of the HBV DNA assay), was observed in 5 out of the 28 subjects on JNJ-56136379 75 mg monotherapy. In addition, there were 2 subjects who met the virological breakthrough threshold but, due to the change of treatment, the virological breakthrough could not be confirmed. The virological breakthrough in these subjects is expected to be associated with viral resistance to JNJ-56136379. An HBV DNA decline was observed in these subjects upon initiation of NA treatment confirming pre-clinical data showing that viral variants resistant to JNJ-56136379 remain susceptible to NA treatment.

Given the virological breakthroughs observed in the JNJ-56136379 75 mg monotherapy arm (Treatment Arm 1), this treatment arm was discontinued early per Protocol Amendment 4. All subjects were to stop further dosing with JNJ-56136379 75 mg, start treatment with NA, and enter the post-treatment follow-up phase (Schedule 1).

In addition, per Protocol Amendment 4, the duration of treatment with JNJ-56136379 250 mg monotherapy has been limited to a maximum of 24 weeks (see Section 6.1). As an additional precautionary measure to safeguard the subjects, a stringent futility rule has been implemented in the JNJ-56136379 250 mg monotherapy arm (see Section 6.2).

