### 7.5.2 Post-Baseline

- ***Time of Viral Breakthrough (if applicable)***

For subjects with viral breakthrough, the incidence of treatment emergent (NGS) and treatment enriched genetic variations will be tabulated in frequency outputs (n, %) and the genetic variations will be listed for all subjects with post-baseline sequencing data.

The return to baseline for subjects with viral breakthrough and treatment-emergent genetic variations at time of viral breakthrough will be tabulated in frequency outputs based on Sanger and NGS data, as well as the treatment-emergent genetic variations in subjects who did not return to baseline.

- ***Other Post-Baseline***

The prevalence of genetic variations at other time points will be tabulated in frequency outputs (n, %), based on Sanger and NGS data (1% and 15% cut-off), and the genetic variations will be listed for all subjects. Time points of specific interest are end-of-treatment and end-of-study.

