- m. Vital signs include supine systolic blood pressure (SBP), diastolic blood pressure (DBP), and pulse rate.
- n. If blood sampling or vital signs measurement is scheduled for the same time point as ECG recording, the procedures should preferably be performed in the following order: ECG(s), vital signs, blood draw.
- o. Biochemistry samples must be taken fasted for at least 10 hours for measurement of phosphorus, calcium, creatinine clearance, and lipids. Subjects should bring their study drug with them to each visit and have that day's intake at the site.
- p. Creatinine clearance (estimated by the estimated Glomerular Filtration Rate [eGFR], which is calculated by the Modification of Diet in Renal Disease [MDRD] formula) will be assessed.
- q. In case a of positive dipstick result, a urine sample will be set aside for additional examination of the positive parameter (eg, quantification as applicable).
- r. Only applicable to subjects in the pharmacokinetic subgroup and subjects enrolled at a site with an on-site Fibroscan device.
- s. Sequencing on Day 1 (predose) will be performed by default if HBV DNA levels are within the ranges required for the sequencing assay; other samples may be sequenced based on the sponsor virologist's request.
- t. In virologically suppressed subjects, available historical data on HBeAg status before start of NA treatment will be collected in the eCRF.
- u. Quantitative HBeAg assessment will only be performed in subjects who are defined HBeAg-positive at screening based on a qualitative HBeAg assay.
- v. Exploratory serology samples may be analyzed at the sponsor's discretion. Samples may be used to assess virologic or serologic markers of HBV.
- w. Sparse pharmacokinetic sampling will be performed for all subjects. One sample predose at all indicated time points (except on Day 1: one sample 2 hours postdose only). Study drug should be taken on site. The time of study drug intake will be recorded.
- x. Approximately 35% of all subjects (at selected sites only) will undergo semi-rich pharmacokinetic sampling (pharmacokinetic subgroup) predose and 2, 4, 12, and 24 hours postdose. The study drug should be taken on site. The time of study drug intake will be recorded.
- y. Approximately 35% of all subjects (at selected sites only) will have 24-hour urine sampling (pharmacokinetic subgroup) during the intervals 0-2, 2-12, and 12-24 hours postdose. This sampling schedule will require an overnight stay on site.

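### SAP 7.1 takes the nearest sequenced sample as the sequence at breakthrough, without limit, so a breakthrough whose own sample was not sequenced can be tabulated as sequenced without emergent substitutions

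*SAP*

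**What the plan says.** SAP 7.1 lists the time points at which genetic variants are analysed. For breakthrough the entry reads "Time Point of Sequence at Viral Breakthrough: time point with virology data available closest to the time point of viral breakthrough (FTPT"), and for relapse "Time Point of Sequence at Viral Relapse: time point with virology data available closest to the time point of viral relapse". Neither entry says whether the sample may precede the event, how far away it may lie, or that it must be post-baseline. Other entries in the same list do carry such limits; the end-of-study sequence, for instance, is the "last available off-treatment post-baseline time point in the study with virology data available". FTPT is not explained there or in the SAP abbreviations.

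Not every sample is sequenced. SAP Appendix 5 says: "Sequencing on Day 1 (predose) will be performed by default if HBV DNA levels are within the ranges required for the sequencing assay". After baseline, SAP 7.1 leaves it to the sponsor virologist, who may trigger sequencing "based on changes in HBV DNA levels observed in each individual subject and the limits of the sequencing assay".

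The selected sample feeds the tables. SAP 7.5.2 states: "For subjects with viral breakthrough, the incidence of treatment emergent (NGS) and treatment enriched genetic variations will be tabulated in frequency outputs". SAP 7.3 asks for the number and percentage of subjects with emergent and enriched substitutions at breakthrough and at relapse. SAP 7.5 sets the denominator as subjects who have sequence data at whichever time point was selected. SAP 7.2 calls a variant emerging when it is below 1% at baseline and at least 15% later, and enriched when it goes from at least 1% but below 15% to at least 15%.

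**The concern.** Emergence of treatment-associated mutations is a secondary endpoint (Protocol 2.1). Protocol 1.3.4 names resistance to JNJ-56136379 as the expected cause of the breakthroughs behind the early closure of Arm 1. The share of breakthroughs that carry new core substitutions is therefore one of the more consequential descriptive results of the study.

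The rule fills the breakthrough row even when the virus at breakthrough was never sequenced. A sample from before the rebound was drawn before the resistant population had grown, so it is unlikely to show the variant at 15%. A sample drawn long after JNJ-56136379 was stopped may miss a variant that has since reverted. Either way a missing result is entered as a negative one. The error also carries forward: the return-to-baseline table in SAP 7.5.2 is restricted to subjects with emergent variants at breakthrough, so a misassigned subject drops out of that table too.

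**Working it through.** The documents give no figure to reproduce. The check applies the rule as written.

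**1. Which sample is chosen when the breakthrough sample has no sequence.** The inputs are the target days in SAP Table 2 (Day 1; Weeks 2, 4, 8, 12, 16, 20 and 24 at days 14, 28, 56, 84, 112, 140 and 168) and the sequencing visits in SAP Appendix 5, which has none at Week 1. All other scheduled samples are assumed to be sequenced.

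- Week 2: Day 1 is 13 days away and Week 4 is 14 days away, so Day 1 is chosen.
- Week 4: Week 2 is 14 days away and Week 8 is 28, so Week 2 is chosen.
- Weeks 8, 12, 16 and 20: the visits before and after are both 28 days away. SAP 7.1 has no tie rule. The one in SAP 2.3 covers two visits in the same analysis window, which is a different case. With visit windows of ±5 days, the direction would depend on actual visit dates.

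If only Day 1 and one later sample are sequenced, Day 1 is nearest when the later sample falls more than (breakthrough day − 1) days after breakthrough: 27 days for Week 4, 55 for Week 8, 83 for Week 12 and 167 for Week 24.

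**2. How a stand-in is scored.** Day 1 compared with itself cannot be both below 15% and at least 15%, so it can be neither emergent nor enriched. A sample from before the rebound can in principle qualify but is unlikely to. Both have data at the selected time point, so both stay in the SAP 7.5 denominator.

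**3. Can the breakthrough sample lack a sequence?** Under SAP 5.3, breakthrough can be declared from just above 200 IU/mL in a subject who had been below the LLOQ (20 IU/mL, SAP 5.1). Once it is confirmed, JNJ-56136379 is stopped (Protocol 10.2, criterion 12). On 75 mg monotherapy, "An HBV DNA decline was observed in these subjects upon initiation of NA treatment". A later sample that can be sequenced may therefore never arise.

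Illustration, with an assumed baseline of 10^6 IU/mL and the mean fall of 2.89 log10 at Day 29 on 75 mg (Protocol 1.1): 10^(6 − 2.89) = 10^3.11 ≈ 1,288 IU/mL at about Week 4. Suppose the assay needs 1,000 IU/mL, which is an assumption. Week 4 could then be sequenced, and a breakthrough that stays at 201 to 1,000 IU/mL could not. If nothing in between was sequenced, a Week 16 breakthrough takes the Week 4 sample: 112 − 28 = 84 days, or 12 weeks, earlier. With a limit at or below 200 IU/mL the problem mostly disappears.

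**4. Size in the table.** Protocol 1.3.4 reports 5 confirmed breakthroughs among 28 subjects, and 2 more that met the threshold but could not be confirmed. SAP 5.3 also accepts a criterion met at the last on-treatment time point as confirmed, so those 2 may count. Assume every breakthrough is resistant and k of them are misassigned.

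| Breakthroughs | k | Rule as written | Unsequenced reported apart |
|---|---|---|---|
| 5 | 1 | 4/5 = 80% | 4/4, plus 1 not sequenced |
| 5 | 2 | 3/5 = 60% | 3/3, plus 2 not sequenced |
| 7 | 1 | 6/7 = 85.7% | 6/6, plus 1 not sequenced |

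One subject is 1/5 = 20 percentage points, or 1/7 = 14.3. With 5 breakthroughs, k could be anything from 0 to 5.

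**The case against.** The strongest reply is that the rule works whenever it is needed most. A rise in HBV DNA is exactly what prompts sequencing. If the breakthrough sample is sequenced, its distance from the event is zero and it is chosen. For the example to arise, an early sample must have been sequenced, the breakthrough samples must have failed, and both the qualifying and the confirming values must have stayed low. This stands as a limit on frequency. It does not change what the rule does when a sequence is missing.

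A reader might infer that baseline will routinely stand in. The documents do not support that. SAP 7.1 lists baseline as its own time point, SAP 7.2 speaks of a later time point, and SAP 7.5.2 is headed as post-baseline. The wording permits a baseline stand-in, but it is the less plausible case.

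A reader might also infer that resistance would vanish from the report. SAP 7.3 tabulates emergent substitutions at end of treatment and at time of failure as well, and lists variants at 1% read frequency for treatment failures. SAP 7.5.3 lists aggregate post-baseline sequences, and a separate virology report is planned. These outputs help if another informative sample was sequenced, but not otherwise. The end-of-treatment entry takes the last available on-treatment sequence, so it can fall back on the same early sample.

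Extending the concern in full to relapse is not supported either. SAP 5.3 requires confirmed HBV DNA of at least 2,000 IU/mL, above the whole range of 200 to 1,000 IU/mL considered for the assay limit.

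Finally, excluding unsequenced cases turns 4/5 into 4/4, and low-level breakthroughs may differ from those that can be sequenced. That is fair, and it is why the excluded count must stand beside the percentage.

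**Conclusion.** The point holds as a defect in a selection rule that can misclassify subjects in a secondary-endpoint table. It is not a demonstrated bias. Nothing else in either document restricts which sample the rule may choose. When the breakthrough sample has no sequence, the likely error is downward, because an earlier sample precedes the rebound and a late one may follow reversion.

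The size cannot be stated, since neither the assay limit nor the number of unsequenced breakthroughs is given. A reader might take 20 points as the expected bias. It is only the weight of one subject in five, and it assumes that all five breakthroughs are resistant; if seven count, the weight is about 14 points. The study is exploratory, with no formal testing, so no confirmatory conclusion depends on this. The change is still worth making because the groups are small and the result bears directly on why Arm 1 was closed.

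**What to change.** In SAP 7.1:

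- Define FTPT as the date of the first HBV DNA value that meets the breakthrough criterion later confirmed under SAP 5.3.
- Take as the breakthrough sequence the first sequenced post-baseline sample on or after FTPT, within a stated window, for example up to the next scheduled visit. This also removes ties.
- If there is none, code the subject as not sequenced at breakthrough. Show that count beside the emergent and enriched percentages, and leave the subject out of numerator and denominator.
- State under the table that the percentage describes only breakthroughs that could be sequenced.
- Use the same wording for relapse for consistency, although relapse is less exposed.

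It would also help to state the HBV DNA limit of the sequencing assay, so that a reader can judge how often the case arises.

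The cost is a few sentences in SAP 7.1, one extra row and a footnote. No new data or sampling is needed. The price is a smaller denominator and a percentage restricted to sequenceable breakthroughs, which the reported count makes visible.
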